# List of abbreviations

CAU Care as Usual

CBT Cognitive Behaviour Therapy

CMHD Common Mental Health Disorders

EQ-5D EuroQol standardised instrument for measure of health

outcome

ESR Electronic Staff Record

GAD-7 Generalised Anxiety Scale-7

GP General Practitioner

HR Human Resource

HTA Health Technology Assessment

IAPT Improving Access to Psychological Therapies

IQRs Inter-quartile Ranges

MI Motivational Interviewing

NHS National Health Service

NICE National Institute for Health and Clinical Excellence

OH Occupational Health

PHQ-9 Patient Health Questionnaire-9

PPI Public and Patient Involvement

QALYs Quality-adjusted Life Years

QOF Quality and Outcomes Framework

RCT Randomised Control Trial

RTW Return to Work

SCIN Skin Care Intervention in Nurses

UK United Kingdom

UNISON UK Public Sector Union

National Institute for Health Research

This project was funded by the National Institute for Health Research [HTA] project number15/107/02

Version control tracker					
Version Number	Date	Amendments (explanation of changes)			
v1.1	19/09/2016	Adjusting Ethics/HRA submission date and minor comments from [name] (see email 16/9/16)			
v1.2	27/09/2016	Table relating to recruitment targets per site added to Phase 3 page 13			
v1.3	18/07/2017	1. Measurement of outcomes a. We have agreed with stakeholders that the primary outcome of the definitive trial (if this study shows that a trial is feasible) should be hours until return to work (RTW) (a continuous outcome) rather than time to return to full work as was originally proposed.  b. Data on sickness absence would be collected both from the electronic staff records and by self-report via the study questionnaires  2. During the development of the intervention it became apparent that we would not be able to avoid contamination between the intervention and control arms if we tried to run an individual RCT. In consultation with stakeholders we considered testing the feasibility of randomising at departmental level within trusts. Therefore we have changed the protocol to allow for four trusts to receive the intervention in some departmental groups and care as usual in other departmental groups (see protocol for fuller explanation)  3. We have added bipolar disorder to our exclusion criteria.  4. Following the updated systematic review and stakeholder meeting, we agreed that we would put less emphasis on motivational interviewing and more on problem solving therapy and collaborative problem solving.  5. We have developed the intervention using the methodology described on the study protocol and the case management approach will now include:  a. Establishment of peer support groups b. Giving workers access to HeadGear (an on-line self-help programme based on CBT principles) c. Development and distribution of an evidence-informed RTW leaflet for the worker and line manager  d. More focus on peer support & self-efficacy e. Consideration of work visits (therapeutic RTW) f. Giving line managers – access to HeadCoach (an on-line manager rraining programme)  6. Referral into the intervention a. We agreed that workers should not self-refer b. We would ask line managers to refer workers directly to case-managers, rather than via occupational health office staff if possible.			
v1.4	06/09/2017	Added two updated intervention flowcharts (one for control and one for intervention arm)			
v1.5	25/01/2018	To allow for the verbal consent to be taken over the phone			
v.1.6	15/02/2018	
 
To allow workers who self-refer to OH to be eligible for inclusion in the study
 
To collect contact details from participants (so that follow up questionnaires can be send to participants via email or post)
 
			

		To promote the role of occupational health service in managing workers who are off sick due to common mental health conditions
v1.7	29/06/2018	
 
Expanding recruitment reach to allow field workers to recruit participants during their first appointments if they are assessed as meeting the inclusion criteria
 
Providing sites with specific working to promote the role of OH and the WBTW study
 
Revising timeline dates
 

V1.8	12/03/2019	
 
Adjusting study end date in section 9.0 (now mid-October 2019
 

### 1.0 Summary of research

**Design:** A mixed methods study to develop and test the feasibility of an intervention to improve return to work in NHS staff who go on sick leave with a CMHD.

Method: The study is divided into 2 phases:

- Phase 1 aims to test the feasibility and acceptability of the intervention in the NHS
  and to assess for contamination if the main trial were to be a randomised controlled
  trial at departmental level.
- Phase 2 finalises the manualised intervention and makes recommendations on the best study design for a future trial.

A significant amount of preparatory work was completed prior to phase 1/2 and a full description of this work can be found in the appendix.

We will carry out phase 1 in six OH departments (study centres). At three study centres, study participants will be assigned either to see an OH nurse who has been trained as a case-manager and will receive the intervention or to see an OH nurse who has not been trained as a case-manager and will receive CAU. At two centres, participants will receive CAU only and at one centre, participants will be assigned an OH nurse who has been trained as a case-manager. This design allows us to test for feasibility of the intervention in a NHS setting and to assess the risk of contamination if a cluster RCT were undertaken.

**Setting:** Six OH departments delivering services to different types of NHS Trusts. **Target population:** NHS staff who have recently been issued with a fit note which includes a CMHD.

**Inclusion criteria:** Staff with a CMHD with or without an associated physical disorder, who have been off sick for more than 7 days and fewer than 90 days. Employee must be off sick when referral made to OH and when completing baseline questionnaire.

**Exclusion criteria:** Staff with a psychotic disorder, bipolar disorder, substance misuse disorder or dementia. Staff under investigation for misconduct or in the process of formal disciplinary action.

**Health technologies being assessed:** Standardised case management delivered by OH nurses following training. The intervention is likely to include identifying barriers to RTW, problem solving, peer-support networking, work-focused CBT, optimisation of clinical treatment and goal setting. An agreed written RTW plan with workplace adjustments, based on discussion between participants and their manager and shared with the participants' healthcare professionals. Regular timed reviews.

### **Outcomes:**

**Feasibility:** Rates of uptake among those eligible to participate; the frequency and nature of protocol violations; completeness of data collection; average consultation times compared to normal and mean number of follow-ups per case; extra line manager and human resource time per consultation compared to normal. Fidelity of the case-manager training.

**Acceptability:** A summary of qualitative findings representing views on the intervention and its assessment expressed by participants, case-managers, HR and line-managers. Reasons for not completing the intervention and any adverse effects.

**Measurements of costs:** Costs of delivering the package of interventions including OH nurse time, participant and manager time and cost of training OH nurses in case management.

**Manual development:** Complete specification of the intervention and standard operating procedures for different settings. A manual for training the case-managers.

**Sample size:** With a sample size of 60 we will be able to estimate a participation rate of 80% to within a 95% confidence interval of +/- 10%. We have allowed for 77 participants, so we are confident that we will have a good precision around the participation, and completion rates.

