# 6.3 Recruitment and sampling:

Before recruitment commences, we will train the centres on how we wish to collect sickness absence data from ESR. We will assist participating OH departments to liaise with their HR departments to ensure that the HR departments accurately record fit notes reporting CMHD onto S10 of the ESR system.

In the study centres where participants receive either the intervention or usual care, two OH nurses will recruit participants at each centre. Up to two OH nurses will be trained in case management and will deliver the intervention and the other will deliver care as usual for that trust. The duration of recruitment will be 6 months. Where possible, all staff who go on sick leave with CMHD during the 6 month recruitment period will be referred to the OH department as soon as their line manager receives a fit note. We will provide sites with wording to further raise the profile of OH and their local site's involvement in the study. The decision on whether to circulate this correspondence will be left to participating sites. The study will also recruit from those who self-refer to Occupation Health departments. All staff who go off sick with CMHD and who are referred to the participating OH departments will be provided with information about the study and invited to participate. Those who wish to participate will be asked to consent and will be screened for eligibility for the study. At the discretion of the participating study centres, participants in the intervention group will continue to receive the

intervention until they RTW or leave their employment, even if they are still on sick leave after the study has finished.

At one study centre (Guy's and St Thomas' NHS Foundation Trust; GSTT) we would like to promote the role of occupational health service in manging workers who are on sick leave due to common mental health conditions. We would like to add a brief message about the role of OH and about the Ways Back to Work study to the Workforce Directorate brief which is correspondence disseminated across the GSTT trust only targeting line managers.

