# 6.4 Data collection and follow up 6.4.1 Quantitative data

Data on sickness absence for CMHD will be collected for six months after the participant enters the study from S10 on the participating centre's ESR and by self-report questionnaire. Study participants will be given a self-administered baseline questionnaire to complete at the time of entry to the study (t=0). They will be sent a follow-up self-administered intermediate questionnaire at three months (T=3) and a final follow-up self-administered questionnaire at six months (t=6) after entry to the study. Note, all participants will complete the same baseline and intermediate questionnaires. Responses provided in the intermediate questionnaire will than determine which version of the final questionnaire will be administered i.e. final questionnaire (version 1) will be administered to those employees who are back at work in any capacity for more than four weeks at the three month time point (T=3); final questionnaire (version 2) will be administered to those who are still off on sick leave at T=3months due to their mental health condition (including those who have not returned to sustained work) or those who did not return the intermediate questionnaire.

Participants will be invited to complete paper-based questionnaires. This will be returned to the central research team using business reply envelopes. A series of reminders will be used to encourage return of the study questionnaires for non-responders. The reminders will include, one email reminder, one telephone reminder and finally a replacement questionnaire will be sent to the participants preferred postal address. To allow to send participants 3 and 6 months questionnaires (and reminders if needed), we will collect contact details from participants (name, surname, mobile phone, email address, home postal address). Contact details will be collected together with the baseline questionnaire.

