# 6.5.1 Quantitative

Rates of recruitment will be calculated from the numbers of eligible participants and of those who agree to participate in the study. Characteristics of eligible participants will be recorded at baseline and will be summarised through means, medians, standard deviations, and interquartile ranges (IQRs). Characteristics will be compared between those who agree to participate in the feasibility study and those who do not. Outcome variables, including anxiety/depression score, health related quality of life score, use of antidepressants, will be summarised separately for baseline and follow-up using means and standard deviations if they are normally distributed, or through medians and IQRs otherwise. Number of days before returning to normal working hours will be summarised by medians and IQRs. For each possible outcome measure, the prevalence of missing data will be quantified. We will calculate the proportion of participants who complete the intervention, and the proportion of completed data sets.

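### Section 6.5.1 judges completeness by the prevalence of missing data, which cannot show under-recording of sickness absence in ESR code S10, and the protocol states no check of S10 against what it already knows

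*Protocol*

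**What the plan says.** The summary (section 1.0, Outcomes) lists "the frequency and nature of protocol violations; completeness of data collection; average consultation times compared to normal" among the feasibility outcomes without saying how completeness is measured. Section 4.2 makes clear that occupational outcomes are included. Section 6.5.1 supplies the measure: "For each possible outcome measure, the prevalence of missing data will be quantified", together with "the proportion of completed data sets".

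Sickness absence has two sources. Section 6.4.1 takes it "from S10 on the participating centre's ESR and by self-report questionnaire" over the six months after entry. Section 2.4 describes S10 as the code for absence due to anxiety, stress, depression and mental health, so the extract is limited to absences placed under that code.

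The protocol recognises that S10 depends on how HR codes. Section 6.3 plans help for centres "to ensure that the HR departments accurately record fit notes reporting CMHD onto S10 of the ESR system", and section 9.0 schedules standardisation of ESR recording for July to October 2017, before recruitment.

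On the participants' state at entry, the inclusion criteria in section 1.0 are explicit: "Employee must be off sick when referral made to OH and when completing baseline questionnaire".

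**The concern.** A questionnaire that is not returned, or an item left empty, is a visible gap, and its frequency is a fair measure of completeness. An extract of S10 spells is a list of events. Three failures leave nothing empty in it: an absence never entered, an absence entered under another code, and a spell with the wrong end date. Counting missing values therefore says little about how much absence the source has captured.

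This matters because Question 7 in section 4.1 asks how well data collection would work in practice, and ESR is one of two candidate sources for the return-to-work outcome in a definitive trial. Section 6.1 also says that Groups B and C will supply outcome distributions for later power calculations. If ESR is carried forward because few of its values are missing, its capture will not have been measured. The training and standardisation steps aim to reduce miscoding, but nothing stated would show whether they succeeded.

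**Working it through.** **What each failure looks like under the stated metric**

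- Questionnaire not returned: a missing value, counted.
- Entry absence not on S10: recognisable, because the participant is known to be off sick. Section 6.5.1 does not say that anyone will look, or how the case is classified.
- Later CMHD absence uncoded or coded elsewhere: no missing value in ESR.
- Wrong end date on a recorded spell: no missing value, but days absent and time to return are wrong.

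The last two can be seen only by comparing ESR with another source. Self-report is available, but no comparison is stated.

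**Inputs**

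- Participants: at most 77 (section 6.6). Table 1 gives five trusts with 14 each and one with 7: 5 × 14 + 7 = 77.
- Share of entry absences on S10: not in the protocol. Assumed range 70% to 95%.
- 95% half-width for a proportion: 1.96 × √(p(1 − p)/n).

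**The protocol's own figure first**

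Section 6.6 says that 60 participants estimate an 80% rate to within ±10 points. The formula gives 1.96 × √(0.8 × 0.2/60) = 0.101, so the figure is reproduced to rounding. The present point does not depend on it.

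**Entry absences without an S10 record, n = 77**

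- 70% captured: 77 × 0.30 = 23.1, about 23 participants.
- 95% captured: 77 × 0.05 = 3.9, about 4 participants.

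At 95% capture, the chance that at least one of the 77 lacks a record is 1 − 0.95^77 = 0.98, taking participants as independent. A check at entry would therefore very probably find something to report even when coding is good.

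**Precision of that check, pooled**

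- 70%: 1.96 × √(0.7 × 0.3/77) = 0.102, about ±10 points.
- 95%: 1.96 × √(0.95 × 0.05/77) = 0.049, about ±5 points.

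**Precision by trust, at 70%**

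- n = 14: 1.96 × √(0.21/14) = 0.240, about ±24 points.
- n = 7: 1.96 × √(0.21/7) = 0.339, about ±34 points.

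The pooled estimate is informative. Intervals by trust are not, so plain counts are enough there.

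**The case against.** The strongest reply is that the protocol never says an empty S10 record is read as attendance or as zero days. Section 6.5.1 counts missing data per outcome measure, not per source. A participant known to be off sick who has no S10 spell has no ESR return date, and an analyst would naturally call that missing. This stands. A reader might infer that ESR missingness will come out at 0 of 77 whatever the true capture, but the documents do not support that. A reader might also calculate how far the median absence would fall if unrecorded people were counted as zero days. That needs an assumed capture rate, an assumed entry day, a curve drawn through one trust's approximate figures, and a zero-coding rule that the protocol does not contain. It could only be an illustration.

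A second tempting inference is that uneven coding across trusts would bias the comparison of Groups B and C. Section 6.1 uses that comparison to look at how participants were managed, as a sign of contamination. It is not a comparison of ESR absence.

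Third, self-report is a second source, and HR support is planned. Both are true and reduce the risk. Neither measures capture: self-report is open to non-response, and no comparison between the sources is stated.

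Fourth, a rule for absent ESR records and an agreement table could sit in a statistical analysis plan, which is not shown. This stands for the details. But the protocol did choose a completeness metric, and applied it to every outcome, including one for which it cannot do the job.

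**Conclusion.** The point holds in a limited form. The prevalence of missing data is a sound measure for questionnaires but cannot show under-recording in S10, and the protocol states no other measure although it has the means for one. The entry absence can be checked for everyone. Later spells and return dates can be checked only against self-report, among responders.

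The size is unknown because no capture rate is given. The figures of 23 to 4 participants out of 77 rest on the assumed 70% to 95% range and on full recruitment. They describe the entry absence only and do not forecast bias in any result. The protocol's quantitative analysis is descriptive, so what is at stake is the recommendation on ESR as an outcome source for the definitive trial. The change is worth making and cheap.

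**What to change.** In section 6.5.1, keep the prevalence of missing data and add the following for ESR:

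1. The proportion of all participants with an S10 spell covering the date of entry, pooled, with a 95% confidence interval and plain counts by trust. A Wilson interval is preferable if capture is near 100%.
2. Agreement of ESR with self-report on return-to-work date and days absent at 3 and 6 months, among questionnaire responders.
3. A rule that a participant with no S10 spell at entry is classed as ESR-missing, not as having zero days absent or as having returned.

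Two practical points need confirming. Section 6.4.1 describes ESR data for the six months after entry, so the extract must include spells already open on the entry date. The questionnaires are not shown, so it should be checked that they ask for a return date and days absent in a form that can be set against ESR.

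The cost is one or two extra descriptive tables and a few sentences. The first check does not reach later spells or end dates. The second does, but is limited by non-response and recall, so disagreement will not by itself show which source is wrong.

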# 2.0 Background and rationale

# 2.1 Why is an intervention needed?

The National Health Service (NHS) is the biggest employer in the United Kingdom (UK) with NHS England alone employing more than one million full time equivalent staff (Taylor 2015). As a whole it performs relatively poorly across many measures of staff health and wellbeing, with sickness absence rates that are 27% higher than the UK public sector average, and 46% higher than the average for all sectors (Chartered Institute of Personnel and Development 2013). Department of Health research has estimated that NHS trusts in England could save

an average of £350,590 per year by reducing sickness absence (Boorman 2009b). Monetary consideration aside, there is an important link between the positive wellbeing of staff and better patient care (Boorman 2009b).

In Britain, common mental health disorders (CMHD), including depression and anxiety are the main causes of sickness absence in the working population (Black 2008) and poor mental health is estimated to account for more than a quarter of staff sickness absence in the NHS (Boorman 2009b, Boorman 2009a). The full cost of mental illness in NHS staff is hard to quantify, since as well as direct financial impacts on the NHS, individual employees and their families incur losses and there is a financial cost to society as a whole. Whilst over 75% of employees who go on sick leave with mental illness do eventually return to work (RTW), (Chartered Institute of Personnel and Development 2011) those who are absent for six months or longer have less than a 50% chance of ever returning to employment (Waddell, Burton 2006).

A recent Cochrane review on workplace interventions to improve capacity for work in people on sick leave found that the quality of evidence on the effectiveness of workplace interventions for workers with mental health problems was low (van Vilsteren et al. 2015). If an intervention in NHS workers who are off work with CMHD could accelerate return to useful work and prevent sickness absence extending to beyond six months, in a way that was cost-effective, there could be major benefits both for the affected worker, their colleagues and for NHS patients.

### **2.2** Proposed form of intervention

Previous work has indicated that interventions to reduce time lost from work due to mental illness are most likely to be effective if multi-faceted (National Institute for Health and Care Excellence 2009, van der Klink et al. 2007, Pomaki et al. 2010). Systematic reviews suggest that an intervention should include identifying barriers to RTW (Waddell, Burton & Kendall 2008), work-focused cognitive behaviour therapy (CBT) (Nieuwenhuijsen et al. 2014), focused problem solving (Arends et al. 2012), optimisation of clinical treatment, goal-setting, a step-wise written RTW plan based on discussion between participants and their manager (Waddell, Burton 2004), workplace adjustments including flexible working and graded RTW, regular timed reviews, and communication of the RTW plan with other healthcare professionals, in particular general practitioners (GPs) who are treating participants (Stern, Madan 2012, Waddell, Burton & Kendall 2008), and maintenance of contact between the line manager and the sick-listed worker (Nieuwenhuijsen, K. 2004). A comprehensive systematic literature search on RTW interventions specifically for workers with CMHD found similar results (Pomaki et al. 2010). That review looked at whether any of the interventions were specific to healthcare, but found that most of the evidence concerned mixed groups of occupations and did not focus on a single sector.

Two important guidelines relevant to the management of workers on sick leave with mental health disorders have been published in the Netherlands and the United Kingdom (UK). The Dutch guideline is specific to mental health conditions (van der Klink et al. 2007). It was first published in 2000, updated in 2007 and the third edition which is currently under development is due to be published in 2016 (Hulshof 2015). The National Institute for Health and Clinical Excellence (NICE) guideline on managing sickness absence applies to all types of illness (National Institute for Health and Care Excellence 2009), and its implementation needs to be tailored to specific conditions and the local context. A few studies have evaluated the use of the Dutch guidelines. A randomised control trial (RCT) comparing the implementation of the first edition (published in 2000) with usual care only showed a decrease in the time to RTW among workers with minor stress disorders, but not in those with other CMHD (Rebergen et al. 2009). An on-going RCT is evaluating the effectiveness of the 2007 Dutch guideline in improving RTW of workers with CMHD by comparing its use by appropriately trained occupational physicians with management by others who have not received such training (van Beurden et al. 2013). In the Netherlands, each employee is required to have a rehabilitation consultation with an occupational physician when they take sick leave beyond a specified period. This is not the case in the UK, where most NHS staff who take sick leave would be seen first by an occupational health (OH) nurse. Therefore, although we will take into account evidence on the Dutch guideline in planning our study, we cannot assume that evidence can necessarily be generalised to NHS workers.

A Norwegian RCT demonstrated that work-focused CBT combined with individual job support for those off work with CMHD led to increased work participation when compared to usual care, especially in those who had been off work for longer than 12 months (Reme et al. 2015). However, the trial was not set in a workplace and the Norwegian Insurance Scheme provides 100% coverage for income lost from mental illness. Thus, the results may not be generalisable to the UK.

Although there have been few studies on this topic in the United Kingdom (UK), one investigation carried out at an English NHS Trust suggested that an intervention could be cost-effective if based on multi-disciplinary case-management delivered by trained OH case managers (who were mainly OH nurses) (Smedley et al. 2013a). Another based in a Scottish health board also used case-management (EASY study). In both studies a bio-psychosocial approach to assessment was a key component of the intervention. The importance of combining workplace and clinical interventions is reinforced by the findings of a recent Cochrane review on interventions to improve RTW in depressed people (Nieuwenhuijsen et al. 2014) and also in a systematic review on characteristics of interventions that facilitate RTW after sickness absence (Hoefsmit, Houkes & Nijhuis 2012).

[figure not shown]
